# 8.1. Formulation and Preparation of Study Drug

XT-150 is a plasmid DNA formulated as a sterile, aqueous phosphate-buffered saline solution.

Table 4: Final Drug Product Quantitative Composition Per Vial

Ingredient	Function	Target Amount per Vial
plasmid DNA	Active ingredient	150 μg/mL or 450 μg/mL
Phosphate-buffered isotonic solution	Solution	

#### 8.1.3. Placebo Formulation

Sterile phosphate-buffered saline (PBS) for injection (two 0.5 mL injections for total of 1 mL) will be the placebo comparator for this study.

Data from pilot studies in animals showed that saline solutions produce no efficacious benefit in a wide variety of pain models. PBS has not demonstrated clinical benefit for pain and is therefore suitable for use as a placebo.

# 8.2. Investigational Product Administration

Investigational product (XT-150 or placebo) will be administered as two bolus, bilateral intraarticular injections into the facet joint. The injection will be performed with fluoroscopic guidance.

## **8.3. XT-150 Blinding**

The Investigator, study staff, and participants will be blinded to the treatment administration. The unblinded pharmacy will provide ready-to-use syringes, coded by participant number to the clinical staff. The Pharmacy will maintain a log in a secure location with the participant number and the assigned lot number of the investigational product. Lot numbers are unique to dosage strengths.

# 8.4. Compliance

Treatment compliance for intra-articular study drugs will be documented in the CRF by recording the date, injection time, and whether the dose of study drug was completely injected.

## 8.5. Previous and Concomitant Medications and Substances

All pain therapy (both medications and treatments) and all prescription and over-the-counter medications and supplements administered within the last month prior to enrollment will be documented in the CRF.

#### **8.5.1.** Prohibited Medications

See exclusion criteria (Section 7.2).

The following treatments are prohibited prior to study drug administration at Day 0 and Day 90:

- Current treatment with antibiotics or antiviral agents (exception: topical treatments)
- Current treatment with immunosuppressive agents
- Current use of systemic steroids (equivalent to >10 mg/day prednisone)
- Current treatment with anticoagulants, other than low-dose aspirin. Patients, if medically feasible, can interrupt anticoagulant therapy by following local medical practice protocol for intra-articular injections for patients on anticoagulant, antiplatelet therapy.

Concomitant medications for pain will be allowed at doses and frequencies prescribed prior to the study treatment. In the event a participant requires additional analgesic treatment during study participation, he/she should take the protocol-specified rescue medication. Introduction of new medications to treat FJOA pain during the study period is prohibited and considered a protocol deviation.

#### 8.5.2. Rescue Medication

Acetaminophen ( $\leq$  3,000 mg in 24 hours) will be allowed as rescue medication during participation in the study. Rescue medication must not be taken within 12 hours preceding any planned post-treatment visit.

# 8.6. Accountability Procedures

The pharmacy or study personnel are responsible for ensuring that all XT-150 study drug shipments, inventory, and use are recorded and accountability is maintained.

The Sponsor's site monitors will be responsible for checking drug accountability at the site. Inventory records must be readily available for inspection by regulatory authorities at any time. Each shipment of study drug will contain an acknowledgment of receipt section for site signature. Upon receipt of study drug, the pharmacy or study personnel will visually inspect the shipment and verify the number and condition of vials or capsules received. Refer to the Pharmacy Manual for additional information.

## 8.7. Study Drug Handling and Disposal

Upon completion of the study, termination of the study, or upon written authorization from the Sponsor, all unused and partially used study drug will be centrally destroyed. All records of disposal by a centralized destruction site will be maintained by the Sponsor.

## 9. STUDY PROCEDURES

Study procedures should be completed within the windows provided in the Schedule of Assessments and Procedures located in Table 1.

A telephone call documenting safety and efficacy assessments may be used for participants unable to physically attend follow up visits due to COVID-19 infection or coronavirus exposure concerns. Home services may be employed for blood collections.

Any nonscheduled procedures required for urgent evaluation of safety concerns take precedence over all routine scheduled procedures.

# 9.1. Screening

Unless otherwise indicated, screening assessments should be performed within 30 days of enrollment.

- Obtain signed informed consent prior to initiating any study-related assessments or procedures
- Obtain a complete medical history and risk factors (e.g., active malignancy, diabetes mellitus, immunosuppression, transplant recipient, trauma, dialysis) and Intensive Care Unit admission and discharge (if applicable)
- Obtain demographics (age, race, gender)
- Obtain history of all pain medications (prescription and non-prescription) and therapies (e.g., physical therapy, acupuncture) and all other medications and supplements (prescription and over-the-counter [OTC]) administered within the last month prior to enrollment
- Confirm severe facet arthropathy of lumbar facets as determined by imaging (e.g., MRI, CT, X-Ray, etc.) to establish an underlying basis of disease, as determined by usual bony and ligamentous signs of osteoarthritis (OA). Use of historical images permitted if obtained within the last 12 months.
- Clinical assessments
  - Conduct complete physical examination, including height and weight (calculate body mass index [BMI]) and examination of the injection site
  - Measure vital signs (temperature and the site collected [oral, rectal, temporal, or tympanic], heart rate, blood pressure, and respiratory rate)
  - Verify VAS ≥50 prior to lidocaine injection to verify eligibility (see Inclusion Criterion #7). A second VAS should be completed post-lidocaine injection to verify participant's reduction in pain is ≥50% (see Inclusion Criterion #5).
- Laboratory Assessments
  - Obtain blood samples for:
  - Hematology tests (complete blood count [CBC] with differential and platelets count),

- HIV, Hepatitis B and C serology with reflex
- Serum pregnancy test for women of child-bearing potential
- Serum chemistry tests (21)
- Lidocaine testing for target facet joint for study drug injection:
  - Diagnostic unilateral injection with approximately 0.5 mL lidocaine solution at the affected level, as determined by imaging (e.g., MRI, CT, X-Ray, etc.) and physical exam, L3-4, L4-5, or L5-S1 (or the three lumbar cephalad to the sacrum in the case of patients with a 6th lumbar vertebral body). The injection will be performed with fluoroscopic guidance, using the ipsilateral oblique projection. A spinal needle will be placed in an intra-articular position, after local anesthesia of the skin and subcutaneous tissues. The patient will be observed for 1 hour after this injection.
  - Retesting may be performed once at the same level or a different level. If retesting
    is performed on the same day as the initial test, the retest should be separated
    from the initial test by at least 1 hour.
- Confirm participant qualification by inclusion/exclusion

# 9.2. Baseline (Day-1 or Day 0)

Baseline assessments may be completed the day before or day of study drug administration, before the XT-150 injection.

- Brief physical exam, including examination of the injection site.
- Obtain any changes from the complete medical history.
- Record any changes or updates in medications, including pain medications (prescription and non-prescription) and therapies (e.g., physical therapy, acupuncture) administered since Screening visit.
- Efficacy assessments
  - VAS score. Verify VAS ≥50.
  - Oswestry Disability Index
  - International Physical Activity Questionnaire (IPAQ) short form
  - SF12
  - Record participant's response to the OA question: "Considering all the ways that facet pain, the pain that brought you into this study, affects you, how are you doing today?" on a scale of 1 to 5, 1 being very good (asymptomatic and no limitation of normal activities) to 5, very poor (very severe, intolerable symptoms and inability to carry out normal activities)
- Clinical assessments

- Measure vital signs (temperature and the site collected [oral, rectal, temporal, or tympanic], heart rate, blood pressure, and respiratory rate)
- Laboratory assessments
  - Obtain serum for analysis of IL-10 protein and anti-IL-10 antibodies
  - Obtain whole blood for plasmid DNA analysis
- Confirm participant qualification by inclusion/exclusion criteria. Enroll participant prior to dosing

## 9.3. Day 0

- Before administration of study drug:
  - Confirm that all study criteria are met (inclusion and exclusion)
  - Brief physical exam
  - Injection site examination
  - Record any ongoing medical observations that occurred since Screening visit
  - Record any new AEs since Screening
  - Record any concomitant medications since Screening including prescription, OTC and herbal medications. Ensure no excluded medications.
- Administer study drug (see Section 8 for details on preparation)
  - Aseptic techniques will be used in the preparation and administration of XT-150
  - Injections will be guided by ultrasound, fluoroscopy or equivalent visualization
  - All injections of study drug must be performed by a specialist who is qualified, trained, and experienced to perform intra-articular injections to the Facet joint.
  - Examine injection site for infections or reactions
- Clinical assessments
  - Monitor Participant for approximately for 4 hours for signs of study drug reaction.
  - Measure vital signs (temperature, heart rate, blood pressure, and respiratory rate) at least once about 1 hour after injection
- Laboratory assessments
  - Approximately 4 hours after administration, obtain whole blood for XT-150 plasmid analysis

## 9.4. Day 90 (±7 days)

- Clinical Assessments:
  - Brief physical exam, including the injection site for infections or inflammation
  - Measure vital signs (temperature, heart rate, blood pressure, and respiratory rate)
- Efficacy assessments
  - VAS score
  - Oswestry Disability Index
  - IPAQ short form
  - SF12
  - Record participant's response to the question: "Considering all the ways that
    Facet pain, the pain that brought you into this study, affects you, how are you
    doing today?" on a scale of 1 to 5, 1 being very good (asymptomatic and no
    limitation of normal activities) to 5, very poor (very severe, intolerable symptoms
    and inability to carry out normal activities)
  - Record changes in drug regimens or pain therapy
- Assess, identify, and record any AEs since last visit
- Record any changes in concomitant medications since including prescription, OTC, and herbal medications.
- Laboratory assessments
  - Obtain urine pregnancy test and evaluate results. Participant must have negative urine pregnancy test prior to dosing.
  - Obtain serum for analysis of IL-10 protein and anti-IL-10 antibodies
- Administer study drug (see Section 8 for details on preparation)
  - Aseptic techniques will be used in the preparation and administration of XT-150
  - Injections will be guided by ultrasound, fluoroscopy or equivalent visualization
  - All injections of study drug must be performed by a specialist who is qualified, trained, and experienced to perform intra-articular injections to the Facet joint.
  - Examine injection site for infections or reactions
- Clinical assessments post-study drug administration
  - Monitor Participant for approximately for 1 hour for signs of study drug reaction
  - Measure vital signs (temperature, heart rate, blood pressure, and respiratory rate) at least once about 1 hour after injection

## 9.5. Between Clinic Visits

# 9.6. Follow Up Visits – Day 7 (±1 day), Day 14 (±1 day), Day 30 (±2 Days), Day 60 (±7 days), Day 120 (±7 days), Day 150 (±7 days), Day 180 (±7 days), Day 210 (±7 days) and Day 240 (±7 days)

Participants who were enrolled in the study prior to implementation of Protocol Version 3.0 08Jun2022 and either are past their Day 90 visit or do not consent to the Day 90 repeat dose will have their End of Study Visit at Day 180. In this situation, participants should complete all of the End of Study / Day 270 Assessments. Refer to Section 9.7.

- Clinical assessments
  - Brief physical exam, including the injection site for infections or inflammation
  - Measure vital signs (temperature, heart rate, blood pressure, and respiratory rate)
- Efficacy assessments
  - VAS score
  - Oswestry Disability Index
  - IPAQ short form
  - SF12
  - Record participant's response to the question: "Considering all the ways that
    Facet pain, the pain that brought you into this study, affects you, how are you
    doing today?" on a scale of 1 to 5, 1 being very good (asymptomatic and no
    limitation of normal activities) to 5, very poor (very severe, intolerable symptoms
    and inability to carry out normal activities)
  - Record changes in drug regimens or pain therapy
- Laboratory assessments
  - Days 7 (±1 day), 14 (±1 day), and 30 (±2 days): Obtain whole blood for analysis of XT-150 plasmid DNA analysis
  - Days 7 (±1 day), 14 (±1 day), 30 (±2 days), 60 (±7 days), and 180 (±7 days):
     Obtain serum for analysis of IL-10 protein and anti-IL-10 antibodies
- Assess, identify, and record any AEs since last visit
- Record any changes in concomitant medications since screening visit including prescription, OTC, and herbal medications.

# 9.7. End of Study Visit – Day 270 ( $\pm 14$ days)

- Clinical assessments
  - Brief physical exam, including height and weight (calculate body mass index [BMI]) and examination of the injection site for infections or inflammation
  - Measure vital signs (temperature, heart rate, blood pressure, and respiratory rate)
- Efficacy assessments
  - VAS score
  - Oswestry Disability Index
  - IPAQ short form
  - SF12
  - Record participant's response to the question: "Considering all the ways that
    Facet pain, the pain that brought you into this study, affects you, how are you
    doing today?" on a scale of 1 to 5, 1 being very good (asymptomatic and no
    limitation of normal activities) to 5, very poor (very severe, intolerable symptoms
    and inability to carry out normal activities)
  - Record changes in drug regimens or pain therapy
- Laboratory assessments
  - Obtain blood sample for serum pregnancy test for women of child-bearing potential
  - Obtain serum for analysis of anti-IL-10 antibodies
- Assess, identify, and record any AEs since last visit
- Record any changes in concomitant medications since screening visit including prescription, OTC, and herbal medications.

## 10. ASSESSMENT OF SAFETY

## **10.1.** Safety Parameters

Safety will be assessed through the evaluation of AEs, vital signs, and serum laboratory data according to the Schedules of Assessments and Procedures presented in Table 1 and assessment of anti-IL-10 antibodies as described in Section 12.

## 10.2. Adverse Events

Medical history will be collected for all participants at the time of informed consent. After consent, all adverse events (AEs)/serious adverse events (SAEs) will be collected through the last study visit on Day 270. All AEs/SAEs that occur during or after the time of study drug treatment will be considered treatment-emergent AEs (TEAEs). The Investigator will assess all AEs and SAEs and will record the following information on the appropriate CRF page and SAE Report Form (as applicable):

- Event term
- Date of onset
- Date of resolution or stabilization
- Severity
- Relationship to study drug
- Action taken with study medication

Medically indicated laboratory tests (emergency or unscheduled tests) should be conducted at the local laboratory. The Investigator should employ best medical judgment in determining how to manage AEs and SAEs. Any questions regarding AE or SAE management should be directed to the Medical Monitor.

# 10.3. Adverse Event Reporting

The Sponsor has obligations for expedited reporting of SAEs meeting specific criteria to worldwide regulatory authorities. Therefore, the Sponsor must be notified immediately regarding any SAE that occurs after informed consent.

All SAEs must be reported to the Medical Monitor or Contract Research Organization (CRO) Drug Safety Team within 24 hours of the investigational site's knowledge of the event.

All SAEs and discontinuations due to AEs will be reported to the IRB based on the IRB's reporting requirements.

The study site will transmit a SAE report to the CRO Drug Safety Team by email or facsimile (email is preferred method) within 24 hours. Contact details will be provided to all sites. An initial report can be made via telephone, but a completed SAE report must still be emailed or faxed within 24 hours of the site's knowledge of the event. The study sites will be provided with SAE report forms wherein the following information is requested.

• Participant identification, Investigator name, and site number

- SAE information: event term, onset date, severity, and causal relationship
- The outcome(s) attributable to the event (i.e., death, a life-threatening AE, inpatient hospitalization, prolongation of existing hospitalization, a persistent or significant disability or incapacity, or other important medical event[s])
- A summary of relevant test results, pertinent laboratory data, and any other relevant medical history
- The first and last dates of study drug administration. NOTE: as this is a double-blind study, SAE reports should not indicate specific study drug assignments
- Indicate if the study drug was discontinued or the study drug administration schedule was modified
- Supplemental information may include the following hospital records: laboratory results, radiology reports, progress notes, admission and emergency room notes, holding and observation notes, discharge summaries, autopsy reports, and death certificates

In addition, relevant CRF pages should be appended to communicate relevant study drug and participant outcome information. The SAE report should be emailed or faxed within 24 hours with as much of the above information as available at the time. The following minimum information is required for reporting an SAE: participant identification, reporting source, the event, and the causality assessed by the Investigator (or medically qualified designee). Supplemental information may be transmitted using a follow-up SAE report and should not delay the initial report. The Sponsor or designee may contact the investigational site to solicit additional information or follow up on the event.

The Investigator must take all therapeutic measures necessary for resolution of the SAE. Any medications or procedures necessary for treatment of the SAE must be recorded on the appropriate pages of the participant's CRF.

## 10.4. Definitions

#### 10.4.1. Adverse Event

An AE means any untoward medical occurrence associated with the use of a drug in humans, whether or not considered drug related. An AE (also referred to as an adverse experience) can be any unfavorable and unintended sign (e.g., a clinically significant abnormal laboratory finding), symptom, or disease temporally associated with the use of a drug, and does not imply any judgment about causality. An AE can arise with any use of the drug and with any route of administration, formulation, or dose, including an overdose.

Facet Joint Osteoarthritis-related events should not be considered or recorded as AEs or SAEs.

Laboratory abnormalities should not be recorded as AEs or SAEs unless they are associated with clinical signs or symptoms, or require medical intervention. However, each laboratory abnormality (e.g., clinically significant changes detected on hematology, or lab chemistries) independent from any underlying medical condition that requires medical or surgical intervention, or that leads to interruption of study drug infusion or discontinuation, must be

recorded as an AE, or SAE if applicable. If the laboratory abnormality is part of a clinical condition or syndrome, it should be recorded as the syndrome or diagnosis rather than as the individual laboratory abnormality. In addition, laboratory abnormalities or other abnormal test assessments that are associated with signs or symptoms must be recorded as AEs or SAEs if they meet the definition of an AE (or SAE) as described above or in Section 10.4.4.

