## 10.4.4. Serious AE or Serious Suspected Adverse Reaction

An AE or suspected adverse reaction is considered "serious" if, in the view of either the Investigator or Sponsor, it results in any of the following outcomes:

- Death
- A life-threatening AE see definition above
- Inpatient hospitalization or prolongation of existing hospitalization
- A persistent or significant incapacity or substantial disruption of the ability to conduct normal life functions
- Congenital anomaly/birth defect in the offspring of a participant who received study drug

Important medical events that may not result in death, be life-threatening, or require hospitalization may be considered serious when, based upon appropriate medical judgment, they may jeopardize the patient or participant and may require medical or surgical intervention to prevent one of the outcomes listed in this definition. Examples of such medical events include allergic bronchospasm requiring intensive treatment in an emergency room or at home, blood dyscrasias, or convulsions that do not result in inpatient hospitalization, or the development of drug dependency or drug abuse.

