#### 10.4.4.1. Serious Adverse Event Definition Clarifications

- Death is an outcome of an AE, and not an AE in itself
- All deaths during study drug administration or up to the follow-up (FU) visit on Day 180, regardless of cause or relationship, must be reported

Page 46 of 65

- "Occurring at any dose" does not imply that the participant is actively receiving study drug at the time of the event
- "Life-threatening" means that the participant was at immediate risk of death from the event as it occurred. This does not include an event that might have led to death, had it occurred with greater severity.
- Complications that occur during hospitalizations are AEs. If an AE prolongs hospitalization, it is a SAE.
- "Inpatient hospitalization" means the participant has been formally admitted to a hospital for medical reasons, for any length of time. This may or may not be overnight. It does not include presentation and care within an emergency department (although an emergency department visit may define a medically important event, which is also considered a SAE).
- The Investigator should attempt to establish a diagnosis of the event based on signs, symptoms, and other clinical information. In such cases, the diagnosis should be documented as the AE or SAE, rather than as the individual signs or symptoms.

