#### 10.5. Adverse Event Classification

## 10.5.1. Relationship to Investigational Drug

The Investigator's assessment of causality must be provided for all AEs (serious and non-serious) (Table 5). An Investigator's causality assessment is the determination of whether there exists a reasonable possibility that the study drug caused or contributed to an AE.

Table 5: Guidelines for Assessing Relationship of Event to Study Drug

Unrelated	There is little or no chance that the Investigational Product caused the AE; other conditions, including concurrent illnesses, progression or expression of the disease state, or a reaction to a concomitant medication best explain the event
Related	The association of the AE with the Investigational Product is unknown, however, the AE is not clearly due to another condition, or a reasonable temporal association exists between the AE and treatment administration and, based on the Investigator's clinical experience, the association of the AE with the Investigational Product seems likely

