## 10.7.2. Localized Signs of Infection or Inflammation at the Injection Site

Events that, in the opinion of the Investigator, may represent localized signs of infection or inflammation at the XT-150 injection site (e.g., pain, erythema, swelling, pruritus, warmth, hematoma, induration) must be recorded as AEs on the CRF. In general, these events will be temporally related to the injection.

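### Protocol 10.4.1 keeps undefined facet-osteoarthritis-related events out of the AE and SAE record, with no exception for serious or drug-related ones

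*Protocol*

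**What the plan says.** The AE definition in Protocol 10.4.1 is broad: it reaches any "symptom, or disease temporally associated with the use of a drug, and does not imply any judgment about causality". A one-sentence paragraph then narrows it: "Facet Joint Osteoarthritis-related events should not be considered or recorded as AEs or SAEs". The laboratory exclusion that follows comes with a limit, since abnormalities are left out only "unless they are associated with clinical signs or symptoms, or require medical intervention". The FJOA sentence has no such limit, and no definition of FJOA-related events appears in either document. SAP 10.7.1 uses a similar phrase, but only for medical history.

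The passages that interact with it are:

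- **Protocol 10.3:** "the Sponsor must be notified immediately regarding any SAE that occurs after informed consent", with a 24-hour limit for the site.
- **Protocol 10.4.4:** seriousness is judged by outcome, in the view of the investigator or the sponsor, and the outcomes include "Inpatient hospitalization or prolongation of existing hospitalization".
- **Protocol 10.5.1, Table 5:** "progression or expression of the disease state" is among the explanations that make an AE Unrelated. The Related row includes an AE whose association with the product is unknown but which has no clear other cause.
- **Protocol 10.7.2:** possible local infection or inflammation at the injection site, with pain, swelling and warmth among the examples, "must be recorded as AEs on the CRF".
- **Protocol 10.4.4.1:** deaths up to the Day 180 visit, "regardless of cause or relationship, must be reported".
- **SAP 10.14.1 and 10.14.3:** AEs are tabulated by severity and relationship, injection-site reactions of Grade 2 or above are AEs of special interest, and eight categories of local sign are summarized by visit.
- **SAP 11:** the planned summary of abnormal physical examinations is dropped because such findings are said to be captured as AEs.

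**The concern.** The primary objective is safety and tolerability. The product goes into the joint that is already painful, so a harmful local effect could look like the disease. A rule that removes disease-attributed events before they are recorded asks the investigator to settle attribution first, under blinding and without a definition, and leaves no AE record for anyone to revisit.

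The programme's own history makes this more than theoretical. Protocol 4.4.6 lists knee pain, next to injection-site reactions, among the AEs considered possibly related to XT-150 in two earlier trials. The facet equivalent could be set aside here as FJOA-related. An event set aside in this way also supplies nothing to the dose-limiting toxicity definition in the synopsis, or to the AE-based reason for termination in section 7.6.

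**Working it through.** There is no sample-size or power figure to reproduce. The check is to take four kinds of event through the rules as written.

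| Event | Rules that reach it | Result if 10.4.1 is followed literally |
|---|---|---|
| Death up to the Day 180 visit | 10.4.4.1 | Reported whatever the cause |
| Pain, swelling or warmth at the injection site that may be local inflammation | 10.7.1, 10.7.2, SAP 10.14.1 and 10.14.3; possibly also the FJOA exclusion | Recorded, graded and rated for causality if 10.7.2 governs; left out if the exclusion does |
| Non-fatal hospitalization for worsened facet pain, attributed to FJOA | General AE definition and the 10.4.4 outcome test, but the exclusion acts first | No AE, no SAE, no 24-hour report, no table entry |
| Non-serious flare after injection, attributed to FJOA though a drug effect is plausible | General AE definition; could meet the Related row of Table 5, but the exclusion acts first | No AE, no grade, no causality rating |

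**Third row.** Section 10.4.4 lets the sponsor as well as the investigator judge seriousness, but an event barred at site level does not reach the sponsor through SAE reporting. Section 10.4.2 defines a suspected adverse drug reaction as a kind of AE, so an excluded event cannot become one. SAP 10.14.1 builds its treatment-emergent and serious tables from recorded AEs.

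**Fourth row.** Table 5 treats disease progression as a reason for a causality rating, which presupposes a recorded event. The exclusion takes the event out one step earlier. It does not say how sure the investigator must be that FJOA is the cause, whereas Table 5 does address an unclear cause.

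**Second row.** Section 6.1 describes the condition itself as inflammation of the facet joint, and the injection goes into that joint. The same pain can therefore satisfy both rules. No protocol passage ranks them.

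**Other sources.** VAS, ODI, the global assessment, back-pain medication (SAP 10.8) and withdrawals (SAP 10.4) all carry some information on worsening. None supplies seriousness, CTCAE grade and causality.

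**Scale.** Each arm has 24 participants (SAP 5.2), so one is 1/24 = 0.0417, or 4.2 percentage points of an arm's incidence. This is an upper limit per omitted participant: SAP 10.14.1 counts a participant once per preferred term and once per system organ class, so someone who already has another event in that row changes nothing.

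**The case against.** The strongest reply is that the exclusion is a deliberate definition, not an inconsistency. A reader might infer that 10.4.1 flatly contradicts 10.3 and 10.4.4. The wording does not support that: both sections act on events already classed as AEs or SAEs, and 10.4.1 decides what enters that class. The conflict is one of effect. Likewise, Table 5 gives generic examples and does not order every expression of FJOA to be recorded, so it is in tension with the exclusion rather than irreconcilable with it. A specific exclusion after a general definition is ordinary drafting, and it avoids counting the VAS outcome again as AEs. All of this stands.

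A reader might also infer that local worsening goes unrecorded altogether. It does not. Section 10.7.2 is mandatory, has a low threshold and is the more specific rule, while 10.4.1 says only should not. Section 10.7.1 makes Grade 2 injection-site reactions, including pain, an event of special interest, and SAP 10.14.1 gives such events their own table and listing. SAP 10.14.3 summarizes local signs and says that site reactions are recorded as AEs. This removes much of the gap, and it limits the consequence of the SAP section 11 rationale, since most findings at the back are summarized there anyway.

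The reply leaves the third and fourth rows of the table unanswered. None of these safeguards reaches a non-fatal serious event, or drug-related worsening, that the site attributes to FJOA instead of recording it as an injection-site event.

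**Conclusion.** The point holds as a limited but real gap in safety capture that should be closed. As written, 10.4.1 can keep a non-fatal serious event attributed to FJOA out of both expedited reporting and the safety tables, and it removes drug-related worsening so attributed before causality is rated. The overlap with 10.7.2 probably resolves in favour of recording, but no protocol passage says so. The SAP section 11 rationale is inaccurate for examination findings attributed to FJOA.

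The conclusion assumes that sites apply the sentence literally. Instructions outside these documents could already narrow it.

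Its size in events is unknown. A reader might infer that the between-arm AE comparison is diluted by a calculable amount. The documents give neither a rate of FJOA-attributed events nor the share that would be left out, so no such figure can be supported beyond the limit of 4.2 points per participant.

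**What to change.** Reconcile the passages with a short addition to Protocol 10.4.1:

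1. The FJOA exclusion does not apply to an event that meets a 10.4.4 seriousness criterion or the existing Table 5 definition of Related. Such events are recorded as AEs or SAEs with a Table 5 causality rating.
2. Section 10.7.2 takes precedence for signs at the injection site.

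In SAP section 11, align the rationale for dropping the physical-examination summary, because findings attributed to FJOA are not collected as AEs under the present wording.

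The exemption should use the Table 5 threshold and not extend to every event whose relationship to the drug cannot be ruled out. With blinded product injected into the painful joint, an investigator could rarely rule it out, so that wider test could nullify the exclusion and would put a second causality standard beside Table 5.

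The cost is a few sentences in the protocol, one corrected SAP entry, and a few additional AE or SAE records. No new visit or assessment is needed, and routine disease symptoms stay excluded.
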